2.3.2.1.2. Task-switching paradigm

There are two shapes (circle, square) and two colors (yellow, blue), four 172 combinations in total. At the beginning of the test, you will see "SHAPE" or "COLOR" 173 (which means that the answer to the question will be based on the shape or color), and 174 175 then a colorful pattern (e.g., yellow square or blue circle) will appear, then answer the 176 question according to the answer you have just seen (shape or color) as soon as possible. Press B for circles, N for squares, B for yellow, N for blue, and finally the average 177 reaction speed is displayed, which is a test of cognitive structure, flexibility, and 178 plasticity in task processing. The whole test takes about 4 minutes[31, 32]. 179

180

2.3.2.1.3. Stroop Test

In this quiz, you will see different colors for different words, but all the answers 181 are based on the colors (no matter what the words are). Press R for red, G for green, B 182 for blue, and Y for yellow; for example, if you see "green in red color", you have to 183

184 press R. The test results comprised a congruent condition, in which the key pressed 185 corresponded correctly to the color on the screen, and an incongruent condition, in 186 which the key pressed corresponded incorrectly to the color name on the screen. At the 187 end of the test, the reaction time will be displayed, which is mainly a test of the ability 188 to inhibit cognitive interference. The whole test takes about 5 minutes[33, 34].

189 **2.3.2.1.4.** Visual search

In the visual search test, participants identified orange "T" s on the screen from upside-down orange "T" s, blue "T" s, and upside-down blue "T" s. When an orange "T" would appear, the participants were required to press the spacebar as quickly as possible. If no orange "T" appeared, the participants were required to not react. The test contains 80 search displays, each containing 5, 10, 15 and 20 items, mainly to test the search ability of dynamic vision. Reaction speed was displayed at the end of the test, and the whole test took about 4 minutes[15, 21, 35].

197 **2.3.2.1.5.** Wisconsin Card Sorting Task

There is a trial-and-error component to this test. You have to answer the questions first and then determine what the question is based on what is right or wrong. The test is presented in a matching mode, where a pattern on the left is matched with one of the four patterns on the right, and the matching criteria are color, shape, and number. During the test, the questions will be changed from time to time, so if you find out the rules and then suddenly get a question wrong, it means that the question has been changed.
The number of errors is displayed at the end of the test to help measure a person's ability
to reason abstractly and to change problem-solving strategies when necessary. The
entire test lasted about 4 minutes[36-38].

207

2.3.2.2. Measure Of Sleep

208 Participants wore a wrist ActiGraph (wActiSleep, Pensacola, Florida, United States) on the nondominant hand for 2 sleep periods, including the sleep on off day and 209 the sleep before the first third night duty. The sleep data were obtained from ActiGraph 210 211 monitors and analyzed by ActiLife software version 6 using the Cole-Kripke algorithm, 212 including eight sleep indices (sleep latency, total counts, sleep efficiency, total sleep time [TST], wake after sleep onset [WASO], number of awakenings, length of 213 214 awakenings, time in bed)[39, 40]. Participants also recorded the time they went to bed and woke up to enable coordinate checks with the actigraphic data. Daily sleep quality 215 216 was measured using a question that was chosen because it was easy to conceptualize, 217 simple to understand, and less burdensome for participants. The question asked was: On a scale of 0-10, with 0 being the worst sleep and 10 being the best, rate the quality 218 219 of the previous sleep[41].

Participants self-reported age, marital status, exercise habits, smoking, caffeine and alcohol consumption, and chronic diseases. Height and weight were measured from which body mass index (BMI) was calculated as weight in kilograms divided by the square of height in meters (kg/m2).

224

225 Statistical analysis

226	All data are presented as averages \pm standard deviations. The Shapiro–Wilk test	-	
227	was used to examine the normality of the data. Cognitive performance, accuracy, and	L	
228	hit reaction time were analyzed through a paired sample t test. Effect sizes were	;	
229	calculated using Cohen's D. Tests were performed (t tests or $\chi 2$ tests) to test for	•	
230	differences at baseline between the two groups. A 2 \times 2 mixed-design analysis of		
231	variance with repeated measures was used to examine the effects of the intervention.		
232	The Bang's Blinding Index (BBI) was used to explore the effectiveness of the blinding		
233	whereas the McNemar test was used in the comparison of the incidence of side-effects	•	
234	between the placebo and caffeine conditions. All data were calculated using SPSS		
235	(version 20, Chicago, IL, USA), and the significance level was $\alpha < 0.05$.		
236			
237			
238	1. Prasad, R. V.; Gupta, S. L.; Swaminathan, S., Evaluation of Cognitive and		
239	Psychomotor Functional Changes in Anesthesiology Residents after 12 hours		

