1	Cognitive Performance Following Caffeinated Chewing Gum in
2	night-shift Emergency Physicians: A Double-blind Randomized
3	Crossover Controlled Trial
4	China Medical University Hospital, Taichung, Taiwan. 404.
5	Document Date: Nov. 13, 2024
6	
7	Project summary
8	This study aimed to examine the impact of caffeinated chewing gum on the cognitive
9	performance of night-shift emergency physicians in a partially sleep-deprived state. A
10	randomized, double-blind crossover controlled experimental design was employed in
11	which fourteen (Age: 29.9 ± 1.44 ; height: 176.5 ± 5.3 ; weight: 78.1 ± 13.4) emergency
12	physicians consumed either caffeinated chewing gum (CAF) containing 200 mg
13	caffeine or a caffeine-free placebo gum (PLA) for 10 minutes at 03:30 am during their
14	first 8-hour night shift after at least one day off, and completed cognitive performance
15	tests before shift, mid-shift (10 minutes after gum chewing), and after shift, including
16	included Corsi block test, Task-switching paradigm, Stroop Test, Visual search, and
17	Wisconsin Card Sorting Task. Sleep quality was assessed subjectively by a single
18	question score, and objectively by ActiGraph for one night on the off day and the last
19	sleep before the first night shift, to evaluate the effect of sleep quality on cognitive

20	performance.
----	--------------

22	Keywords: Reaction time, cognitive function, Stoop test, Visual search, Patient safety
23	
24	
25	
26	

27 Introduction

A substantial body of research has demonstrated that the cognitive function of night shift doctors declines significantly before work [1-4], particularly in the context of the first consecutive night shift [5]; This raises concerns about the potential impact on patient safety. Consequently, there has been a significant focus on night shift scheduling and working hours [6], to identify the most appropriate rotation method and working hours for emergency physicians to ensure patient safety [7].

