96	experimenting knew which group the subjects were assigned to or what type of gum
97	they were assigned. Once the data has been collected, it will be forwarded to the group's
98	statistical analyst for statistical analysis, who was also unaware of the group
99	assignments. At least one week before the formal experiment, all subjects participated
100	in three to five familiarization tests for the cognitive function tests. Sleep quality was
101	also assessed subjectively by a single question score, and objectively by ActiGraph for
102	one night on the off day and the last sleep before the first night shift. The primary
103	outcome was the results of cognitive function tests, and the secondary outcome was the
104	sleep quality.

106 2.2. Participants

107 Fourteen healthy male emergency physicians were recruited in this study and

based on previous research on caffeine in e-sport athletes [17, 18], we used the G*power 108 3.1 software 24 to achieve an alpha value of 5% and a power of 0.8, which was 109 110 sufficient for the study with only six subjects. However, due to the lack of relevant studies on the effects of caffeine and caffeinated chewing gum on cognitive functioning 111 in night-shift healthcare workers, reference was made to a recent study that examined 112 the cognitive performance of emergency physicians after 24 consecutive hours of on-113 call duty, which included 13 subjects [3]. Therefore, it should be adequate to interpret 114 115 the data derived and statistics from the study.

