On the day of the formal experiment, participants had breakfast and lunch at 08:00 and 12:00, respectively. The participants arrived at the office at approximately 23:20 for the experiment. A brief explanation was given and the cognitive test was administered at 23:30, which took about 20 minutes to complete, after which the subjects were ready to go to work. At 03:30, according to the randomized results, the subjects were given two pieces of caffeinated chewing gum at an absolute dose of 200 mg (Military Energy Gum®, Ford Gum and Machine Go, Akron, NY, USA) (CAF trial) 146 or two pieces of similar looking and tasting placebo gum that did not contain caffeine (xylitol, lime mint, green; Lotte, Saitama, Japan) (PLA trial). After 10 minutes of 147 148 chewing, cognitive function tests were administered. Finally, the last cognitive function tests were performed after duty at 08:20. All subjects used a dedicated computer with a 149 screen frame rate of at least 240 Hz and a mouse response rate of 1ms. 150 151 To explore the validity of the blinding method, we asked the participants (before and after the test) to identify the supplements they ingested. To do this, the question 152 was as follows: "Which supplement do you think you ingested?" There are three 153 possible answers to this question: (a) caffeine; (b) placebo; and (c) don't know. 154 155 Furthermore, the occurrence of side effects or complications was recorded during the 156 trial.

157 **2.3.2.** Outcome measure

158 2.3.2.1. Cognitive function tests

159 Subjects were sequentially given five tests: Corsi block test, Task-switching 160 paradigm, Stroop Test, Visual search, and Wisconsin Card Sorting Task. All the above 161 cognitive function tests were conducted using Psych/Lab for Windows. Measures used 162 in the literature have satisfactory reliability and validity[27].

163 **2.3.2.1.1.** Corsi block test

164 There will be 9 purple squares in the screen, when the test starts, it will flash a

165 number of them randomly in yellow color (the more the number increases), then you will hear "Go", then you have to click the order of the flashing ones, and then press 166 "DONE" in the lower right corner. The smiley face means correct, the crying face 167 means wrong. The maximum number of correct answers will be displayed at the end of 168 the test, which is mainly to test the ability of situational awareness and working memory. 169 170 The whole process takes about 2 minutes[28-30].

171

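### Section 2.3.2.2 sets the second ActiGraph sleep before a 'first third' night duty, and the two stated uses of the sleep data need sleeps on opposite sides of the 03:30 gum

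*Combined protocol and SAP*

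**What the plan says.** Four places in the combined protocol and SAP bear on this.

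- **Project summary.** The second recorded sleep is the last "sleep before the first night shift, to evaluate the effect of sleep quality on cognitive" performance. Gum is chewed at 03:30 during the first 8-hour night shift after at least one day off.
- **Introduction, last paragraph.** Sleep was monitored to see whether caffeine changed the sleep that came afterwards.
- **Section 2.1 (Design).** ActiGraph covers "one night on the off day and the last sleep before the first night shift". The same section makes sleep quality the secondary outcome and lists subjective and objective sleep quality among the things compared between CAF and PL.
- **Section 2.3.2.2 (Measure Of Sleep).** The device is worn "for 2 sleep periods, including the sleep on off day and" "the sleep before the first third night duty". Participants also noted when they went to bed and woke, as a check on the device data.

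The Statistical analysis section names no sleep variable. It does not say whether sleep is an outcome, a covariate or a descriptor.

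**The concern.** Section 2.3.2.2 is the operational text: it tells staff and participants which sleep to record. A duty cannot be both the first and the third of a run, so the instruction has to be interpreted before it can be carried out. The two words lead to sleeps on opposite sides of the intervention.

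Only two sleeps are recorded per trial period, and one is the off-day sleep. The unclear one is therefore half of the objective data for the secondary outcome. If it precedes the tested shift, it is a baseline measure that can help to explain performance but says nothing about what the gum does to sleep. If it follows the gum, it can carry a gum effect but cannot explain cognition already measured. A reader of the sleep result would not know which was estimated. The stated purposes do not settle it, because one needs the earlier sleep and the other a later one.

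**Working it through.** The documents give no figure to reproduce, so the check sets the texts side by side and places each reading on a timeline.

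**Inputs from the documents**
- Pre-shift test at 23:30, gum at 03:30 and last test at 08:20 after duty (section 2.3.1).
- Gum on the first 8-hour night shift after at least one day off (Project summary).
- Two recorded sleeps (section 2.3.2.2).
- Fourteen participants, each with a CAF and a PL period (sections 2.1 and 2.2).

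**Assumption, not in the documents.** For the 'third' reading only, duties run about 00:00 to 08:00 on consecutive nights. This is inferred from the 8-hour shift and the 23:30 and 08:20 tests.

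**Reading 'first'**
1. The sleep ends before the 23:30 test.
2. From 23:30 to 03:30 is 4 h, so it ends at least 4 h before the gum.
3. It is a pre-treatment measure. If nothing carries over across the washout of at least four weeks, any CAF minus PL difference in it is chance.
4. It suits the Summary's purpose. It cannot serve the Introduction's aim or the CAF versus PL comparison in section 2.1.

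**Reading 'third'**
1. Duty 2 ends at 08:00 on the day after the gum: 24 h + 4.5 h = 28.5 h after the gum.
2. Duty 3 starts at 00:00 on the following night: 28.5 h + 16 h = 44.5 h after the gum.
3. The sleep falls between those points. It follows the rest of the gum duty and one further full duty (duty 2).
4. It is a post-treatment measure. Cognition on the first night is complete by 08:20, so this sleep cannot predict it. Any gum effect on it could be diluted or modified by duty 2, which is present in both the CAF and the PL period.

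**The sleep that neither reading records.** The first sleep after the gum starts after the 08:20 test, at least 4 h 50 min after 03:30, and ends before duty 2. It is the most direct test of the Introduction's aim, yet neither reading of the second ActiGraph period captures it.

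**Purposes against readings**

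| Stated purpose | Sleep needed | 'First' | 'Third' |
|---|---|---|---|
| Explain cognition on the tested shift (Summary) | before the shift | yes | no |
| Effect of gum on later sleep (Introduction); CAF vs PL sleep quality (2.1) | after the gum | no | in part |

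No single choice of the second sleep meets every stated purpose.

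**Size of the check.** 14 participants × 2 periods = 28 sessions at most.

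**The case against.** The strongest reply is that this is a drafting remnant. The phrase keeps the word 'first', two other places say 'first' cleanly, and the Summary's purpose fits only a pre-shift sleep. Nothing else in the documents mentions a third duty, a run of consecutive nights, or any procedure after 08:20. The bed and wake records allow the actual sleep to be identified afterwards, and the primary outcome is unaffected.

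Most of this stands. 'First' is the likelier intent, and the harm is largely recoverable. What it does not answer is the conflict of purposes. Reading the phrase as 'first' removes the garble but leaves the Introduction's aim and the CAF versus PL sleep comparison resting on a second recorded sleep that the gum could not have affected.

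Stronger conclusions are tempting, and the documents do not support them:
- A reader might infer that the device was in fact worn after the gum, or that some participants followed one section and some the other. Nothing in the text shows either.
- A reader might say that a third-duty sleep comes two duties after the gum. That counts the gum duty as one of the two; only one full duty lies between.
- A reader might want a loss of power. The plan specifies no sleep analysis and no sleep–cognition correlation, and it gives no effect size for sleep, so any such figure would be invented.

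**Conclusion.** The inconsistency is real and lies in current operational text, but it is minor and confined to the secondary outcome. It affects one of the two ActiGraph sleeps per period and determines whether that sleep is a baseline measure or a post-treatment one. No numerical effect on the results can be derived from the documents.

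That the 'first' reading is pre-gum follows directly from the stated clock times. The 28.5 to 44.5 h window for the 'third' reading depends on the assumed consecutive 00:00 to 08:00 duties. With a different roster the window would move, but the sleep would still follow the gum. The reading of 'first' as the likelier intent is a judgement from two clean statements against one garbled one; only the recordings can confirm it.

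**What to change.** 1. Reconcile the Project summary, the Introduction, section 2.1 and section 2.3.2.2 to one sleep period, and state its timing relative to the 03:30 gum.
2. Before unblinding, use the ActiGraph timestamps and the recorded bed and wake times to establish which sleep was captured in each session.
3. If it was the pre-shift sleep, correct section 2.3.2.2 to the wording of section 2.1. Use the sleep only as a baseline descriptor or covariate, and withdraw the claim to test a gum effect on later sleep.
4. If it was a post-gum sleep, correct the Summary and section 2.1 instead, and do not use it to explain first-night cognition.
5. Analyse any recordings of the other type separately, and do not pool them.
6. State the role of sleep in the Statistical analysis section, which is now silent on it.

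The cost is a few corrected sentences and a timestamp check on at most 28 sessions, using data the plan already collects. The downside is that a few recordings may be lost from the chosen sleep variable and the sleep conclusion becomes narrower.

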63	improving their problem-solving abilities through caffeine.
~ ^	

Graham Marsden and John Leach also found that caffeine improved visual search performance in experienced navigators [21], which may also be related to emergency physicians' ability to search for lesions on diagnostic clues and medical images. In addition, caffeine has been shown to improve performance and cognitive functioning in shift workers in a review of the literature [24]. In recent years, caffeine chewing gum has been marketed to facilitate and accelerate caffeine intake [25], and studies have

70	examined the effects of caffeine gum on cognitive performance in e-sports players [17].
71	However, no studies have been conducted on the effects of caffeine supplementation on
72	cognitive functioning in night-shift emergency physicians with caffeinated chewing
73	gum.
74	This study aims to investigate whether caffeine supplementation with caffeinated
75	chewing gum can be used by emergency physicians during night shifts to maintain
76	proper cognitive functioning and thus patient safety. At the same time, sleep monitoring
77	was performed to observe whether caffeine supplementation affected subsequent sleep.
78	This is to provide emergency physicians with a reference for caffeine supplementation
79	with caffeine gum during night shift work.
80	
81	2. Methods
82	2.1. Design
83	This experiment was a double-blind, repeated-measures, crossover design
84	according to the guidelines of CONSORT 2010[26] and was divided into either a
85	caffeine trial (CAF) or a placebo trial (PL). To eliminate the impact of individual
86	physical differences, a crossover trial was conducted with the same group of subjects.
87	Randomized groups were created using Microsoft 365-Excel (Microsoft, Redmond,
88	Washington, United States), and allocation was randomized and unpredictable. Each

89	trial was separated by at least four weeks to avoid interactive effects. This study
90	compared CAF and PL trial to determine the effects of caffeinated chewing gum on
91	cognitive performance in emergency physicians engaged in night shift work., and
92	subjective, objective sleep quality. Caffeinated chewing gum and placebo chewing gum
93	are very similar in appearance, color, size, shape, and flavor and are difficult to
94	distinguish. The randomization was carried out by a research assistant, with another
95	resident performing the experiment, and neither the subjects themselves nor the resident

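### The secondary outcome of sleep quality is nine measures over two sleeps, with one 0.05 level, no lead measure and no test assigned to it; the sleep meant as the outcome must be settled first

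*Combined protocol and SAP*

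**What the plan says.** All references are to the combined protocol and SAP.

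- **Status of sleep (2.1 Design).** The primary "outcome was the results of cognitive function tests, and the secondary outcome was the" quality of sleep. No index is chosen to represent it.
- **Comparison intended (2.1 Design).** The study "compared CAF and PL trial to determine the effects of caffeinated chewing gum on" cognitive performance, and the same sentence goes on to subjective and objective sleep quality. A comparison of sleep between gums is therefore stated.
- **Measures (2.3.2.2).** The actigraphy output is given as "including eight sleep indices (sleep latency, total counts, sleep efficiency, total sleep time [TST], wake after sleep onset [WASO], number of awakenings", followed by length of awakenings and time in bed. The subjective item reads "On a scale of 0-10, with 0 being the worst sleep and 10 being the best, rate the quality" of the preceding sleep.
- **Occasions (2.3.2.2).** The device is worn "on the nondominant hand for 2 sleep periods, including the sleep on off day and" a second sleep before a night duty.
- **Decision rule (Statistical analysis).** The closing sentence, "version 20, Chicago, IL, USA), and the significance level was" 0.05, sets one level for everything. The paired t test is assigned to cognitive performance, accuracy and hit reaction time. Baseline differences get t or chi-square tests, and intervention effects in general get a 2 x 2 mixed analysis of variance. Sleep is not mentioned.

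**The concern.** An outcome that is named once but measured nine ways gives nine chances per sleep to find a difference between gums. Nothing in the plan says which of them decides the question, so any one result below 0.05 could be reported as an effect of the gum on sleep quality.

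The direction is open as well. A longer time in bed can raise total sleep time while also raising wake time after sleep onset and the number of awakenings. One data set could then be described as better, worse or unchanged sleep, depending on the index quoted.

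The Introduction offers the results as guidance to emergency physicians who use caffeine gum on night shifts. A chance finding on sleep could enter that guidance as if it carried a 5% error rate.

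**Working it through.** **Inputs from the document**
- Measures: 8 actigraphy indices + 1 self-rating = 9 (2.3.2.2).
- Sleeps per trial: 2, so up to 9 x 2 = 18 comparisons of caffeine with placebo.
- Level: 0.05, no adjustment (Statistical analysis). Sidedness is not stated; two-sided is assumed.
- Participants: 14, crossover (2.2), so a within-person comparison has 13 degrees of freedom.

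**Inputs not in the document**
- Correlation among the within-person differences: assumed, range 0 to 0.9.
- Form of the sleep test: assumed to be a paired t test on each measure.

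**The plan's own figure.** There is none for sleep. The sample-size statement in 2.2 (six subjects at 5% and power 0.8) does not refer to it, so there is nothing to reproduce.

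**Independent comparisons.** With all null hypotheses true, P(at least one p < 0.05) = 1 - 0.95^k.
- k = 9: 1 - 0.6302 = 0.370.
- k = 18: 1 - 0.3972 = 0.603.

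**Correlated comparisons.** Null trials were simulated with 14 normal within-person differences per measure and a common correlation. Each measure was tested by a two-sided paired t test at 0.05.

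| Common correlation | 9 comparisons | 18 comparisons |
|---|---|---|
| 0 | 37% | 60% |
| 0.3 | 33% | 52% |
| 0.5 | 28% | 42% |
| 0.7 | 21-22% | 30% |
| 0.8 | 18% | 23% |
| 0.9 | 13% | 16% |

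The 18-comparison column applies the same correlation across the two sleeps. With 0.5 within a sleep and 0 between sleeps, the figure for 18 is 48%.

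**Relative to 5%.** At 0.9 the ratios are 13.3/5 = 2.7 and 16.0/5 = 3.2. At 0.5 they are 28/5 = 5.6 and 42/5 = 8.4.

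**After a change.** One pre-named measure at one sleep: 5%. Nine measures with the level split equally (0.05/9 = 0.0056 each), independent: 1 - (1 - 0.0056)^9 = 4.9%. Holm starts at that same threshold.

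**Which sleep is the outcome.** The sections do not agree.
- The Introduction says sleep was monitored to see whether caffeine affected the sleep that came after it.
- The Project summary and 2.1 place the recordings on the off day and at the final sleep ahead of the first night shift.
- 2.3.1 gives the gum at 03:30 during the shift, and the Project summary puts that shift after at least one day off. The pre-shift sleep therefore precedes the gum, and the off-day sleep appears to as well.
- 2.3.2.2 describes the second sleep with wording that names a first and a third night duty at once, so it does not settle the matter.

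**The case against.** **The comparisons are inferred.** No test is assigned to sleep by name, so a reader might infer 18 planned paired t tests, and the documents do not support that. A gum-by-sleep analysis of variance is another reading, though a main effect and an interaction for each of nine indices is again 18 gum-related tests. Pre-shift sleep might instead fall under the baseline tests. The self-rating is called daily, so even its number of occasions is uncertain. This stands: the counts of 9 and 18 are conditional. It does not help the plan, because an unspecified analysis leaves more to be chosen after the data are seen.

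**The size depends on correlation.** A reader might take 28% to 42% as a property of the plan, or say the inflation is always at least 3.5 times. Neither is supported. The first needs a common correlation of 0.5; the second fails at 0.9. Several indices overlap, so strong correlation is plausible. Modelling that overlap would need definitions and spreads that the document does not give.

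**Timing is more basic than multiplicity.** This stands. If both sleeps precede the gum, even a single pre-named index could not show a gum effect. It does not rescue the present plan either: apart from carryover across the gap of at least four weeks, every null hypothesis would then be true, and any significant difference would be chance.

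**Sleep has another role.** The Project summary also treats sleep quality as something that may explain cognitive performance. That purpose is real, but 2.1 still makes sleep an outcome compared between gums.

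**It is only secondary.** This is correct, and it limits the severity.

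**Conclusion.** The point holds in conditional form. Sleep quality is a named secondary outcome made up of nine measures over two sleeps. It is to be compared between gums, and a single 0.05 level is the only rule.

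If each measure is tested between gums at two-sided 0.05, the chance of at least one false sleep difference runs from about 13% to 37% for nine comparisons. For eighteen it runs from about 16% to 60%, over common correlations from 0.9 down to 0. Every value in that range exceeds 5%, but where the trial falls within it cannot be known from the document.

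A reader might infer that the trial's main result is compromised; it is not, because cognitive performance is a separate outcome family. A reader might also infer that naming a lead index cures the problem. It does so only if the named sleep follows the gum, and the sections conflict on that. The change should be made, but the primary conclusion does not depend on it.

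**What to change.** 1. Reconcile the Introduction with the Project summary, 2.1 and 2.3.2.2, so that the document states which sleep is the outcome and whether it comes before or after the gum.
2. **If a recorded sleep follows the gum:** in 2.1 and the Statistical analysis section, name one lead sleep measure for that sleep. Test it caffeine versus placebo within person at two-sided 0.05. Label the self-rating, the other indices and the other sleep as exploratory (with the self-rating moved out of that list if it is chosen as lead). Report these as paired differences with 95% intervals and no claim of effect. If all nine measures are to remain tests, apply Holm across them.
3. **If both recorded sleeps precede the gum:** report them descriptively, as a check of comparability before dosing or as covariate data, and draw no conclusion about an effect of the gum on sleep.

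The cost is a few sentences, with no new data or participants. The small downside is that an isolated significant result on a non-lead index can no longer be claimed as an effect on sleep quality.

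### Primary cognitive outcomes: a paired t test with no period term, beside a 2 × 2 mixed ANOVA whose factors and priority are not stated

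*Combined protocol and SAP*

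**What the plan says.** Section 2.1 (Design) describes a crossover in which every physician takes both gums ("physical differences, a crossover trial was conducted with the same group of subjects"). The nights are spaced by a washout ("trial was separated by at least four weeks to avoid interactive effects"). Allocation is described only by the software ("Randomized groups were created using Microsoft 365-Excel (Microsoft, Redmond") and by a statement that it was random and unpredictable. No blocking and no target number per sequence is given. The same section makes the cognitive test results the primary outcome and provides practice beforehand ("in three to five familiarization tests for the cognitive function tests").

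The Project summary gives three test times per night ("tests before shift, mid-shift (10 minutes after gum chewing), and after shift, including"). Section 2.3.1 places the first at 23:30, before any gum.

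The Statistical analysis section assigns cognitive performance, accuracy and reaction time to one test ("hit reaction time were analyzed through a paired sample t test"). It then compares "differences at baseline between the two groups" and adds a 2 × 2 mixed-design ANOVA ("variance with repeated measures was used to examine the effects of the intervention"). No period or sequence term is named anywhere.

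**The concern.** Two things are left open.

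**The deciding analysis is undefined.** Two analyses are written for the intervention effect, with no order between them. For neither does the text say whether the score is raw or a change from 23:30, or which test time is used. The layout is also unclear. A mixed design needs a between-subject factor, yet the same physicians receive both gums. A baseline comparison of two groups does not fit a crossover. A two-level time factor would leave out one of the three test times. This part of the concern needs no assumption.

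**A period shift is not provided for.** If scores differ between the first and second study night for reasons other than the gum, the paired t test absorbs that shift. Practice is a plausible source. If each familiarization test is one run of the battery, physicians start the first night after 3 to 5 runs. They start the second after 6 to 8, because the first night adds three. Familiarization reduces this effect but does not exclude it. The four-week gap is aimed at carry-over and does not by itself remove a period shift. At stake are power and, if the two sequences are of unequal size, the caffeine estimate itself.

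**Working it through.** **Inputs.** From the documents: n = 14, alpha 5%, a target power of 0.8, and two conditions per physician. Not in the documents, so assumed: the period effect π (0 to 0.8 SD of the paired difference), the sequence split (7:7 to 10:4) and a two-sided test. The plan has no figure of its own on this point. Its one power statement (six subjects suffice) gives no effect size. It would need a standardized paired effect of about 1.435 two-sided or 1.186 one-sided, so it supplies no input here. The true effect is therefore set at 0.81 SD, which gives the paired t test 80% power at n = 14.

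**Model.** Let D = CAF − PLA for one physician, with residual SD 1. D = τ + π + e if caffeine came second, and D = τ − π + e if it came first.

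**Bias of the paired t test, given the split.** The mean of D is τ + π(n1 − n2)/14, where n1 physicians had caffeine second.
- 7:7: π × 0/14 = 0 for every π.
- 9:5, π = 0.5: 0.5 × 4/14 = 0.14 SD.
- 10:4, π = 0.5: 0.5 × 6/14 = 0.21 SD; with the split reversed, −0.21 SD.

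**Why power can fall at 7:7 without bias.** The shift of ±π enters the sample variance of D, whose expectation becomes 1 + (14/13)π². At π = 0.5 this is 1 + 1.077 × 0.25 = 1.27. The true variance of the mean stays 1/14, so the test becomes conservative.

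**Cost of adjusting.** The period-adjusted estimate is the average of the two sequence means of D, with variance (1/4)(1/n1 + 1/n2), against 1/14 = 0.0714 for the simple mean.
- 7:7: 0.25 × (1/7 + 1/7) = 0.0714, ratio 1.00.
- 9:5: 0.25 × (1/9 + 1/5) = 0.0778, ratio 1.09.
- 10:4: 0.25 × (1/10 + 1/4) = 0.0875, ratio 1.225.

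One residual degree of freedom is also lost (12 instead of 13).

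**Simulation** (200,000 trials per cell; adjusted type I error is about 5% throughout):

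| Split | π (SD) | Paired type I error | Paired power | Adjusted power |
|---|---|---|---|---|
| 7:7 | 0 | 5% | 80% | 79% |
| 7:7 | 0.25 | 4% | 78% | 79% |
| 7:7 | 0.5 | 3% | 72% | 79% |
| 7:7 | 0.8 | 1% | 60% | 79% |
| 9:5 | 0 | 5% | 80% | 76% |
| 9:5 | 0.5 | 5% | 86% or 55% | 76% |
| 10:4 | 0 | 5% | 80% | 71% |
| 10:4 | 0.5 | 8% | 91% or 46% | 71% |

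Where two powers are shown, they depend on which sequence is larger. At 7:7 the two methods break even at about π = 0.15.

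**If allocation was simple (assumption).** From the binomial with 14 trials, P(7:7) = 21%, P(9:5 or worse) = 42% and P(10:4 or worse) = 18%. Averaged over the possible splits, type I error is 5% for both methods. Paired/adjusted power is 80/76% at π = 0, 78/76% at 0.25, equal at about 0.32, and 71/76% at 0.5.

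**Effect of the undefined score.** If the paired t test uses change from 23:30, the part of the shift already present at 23:30 cancels. At 10:4 and π = 0.5 the bias is 0.5 × (1 − share) × 6/14, which is 0.21, 0.11 or 0 SD when none, half or all of the shift is present at 23:30.

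**The case against.** The strongest reply is that the plan may already contain the remedy. A mixed design has a between-subject factor, and when everyone receives both gums the only randomized one is sequence. Sequence × treatment is a 2 × 2 layout, and it separates a period shift from the treatment effect. The ANOVA is also the analysis tied in words to the intervention effect, which hints at priority. This carries weight as the best-fitting reading. It does not settle the matter, because no factor is named, the two-group baseline wording points elsewhere, and the paired t test is assigned to the same outcomes.

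It is also true that the paired t test is valid over randomization, that the documents do not put the period effect above the break-even, and that a balanced list is as compatible with section 2.1 as simple allocation. These points stand and limit the weight of the period argument.

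Several stronger readings are tempting, and the documents do not support them:
- *The caffeine estimate is biased.* Bias needs both a period effect and an unequal split, and neither is reported.
- *Omitting period always costs power, even at 7:7.* Below about 0.15 SD it does not.
- *Two unranked tests nearly double the false-positive rate.* The 8.5–9.5% chance that at least one test is significant arises only if the ANOVA is treatment × time. Both of those factors are within subject, so that reading fits a mixed design less well. Under sequence × treatment with no period effect the figure is 5.4% at 7:7 and 6.9% at 10:4.

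**Conclusion.** The point holds as a failure to commit. The text does not fix the score, the test time, the ANOVA factors or the deciding analysis for the primary outcomes, and it does not commit to handling a period effect. That much follows from the wording alone.

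The period consequence is conditional on the assumed effect sizes and splits. At 7:7 it is a loss of power only, about 7 points at 0.5 SD. At 10:4 and 0.5 SD it is a bias of 0.21 SD in either direction, with type I error of 8%. A reader might infer that the paired t test is invalid or that the trial's result is wrong, but neither follows. The plan should be changed because a better analysis is available from data already collected, at a modest and known cost. Confidence is medium, because the period effect and the split are unknown.

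**What to change.** For each cognitive outcome, name one period-adjusted crossover analysis as the main one: treatment, period and sequence as fixed effects and subject as random. The comparison of CAF − PLA differences between the two sequences is equivalent, and a sequence × treatment ANOVA does the same if that is what was meant. State whether the score is raw or change from 23:30, and which test time is analysed. Report the number of physicians in each sequence. Keep the paired t test as a sensitivity analysis.

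The Project summary already gives observed participant characteristics and the analysis text is in the past tense, so data may be in hand. If outcome data have been seen, label the choice of main analysis as made after data review.

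The cost is wording and one reported count, with no new data. With no period effect, the period term costs under 1 point of power at 7:7, about 4 at 9:5 and 9 at 10:4. Under assumed simple randomization the average cost is about 4 points, with break-even near 0.3 SD.
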